11.3. Device-Relatedness

An AE or SAE that is definitely or possibly related to the device or the insertion procedure should be considered device-related. A serious adverse device effect (SADE) is an event that meets any of the above SAE criteria and is considered related to the device or the insertion procedure by the Investigator. All other events considered related to the device or insertion procedure are non-serious adverse device effects (ADEs).

If it is not certain that an event meets the above definitions, contact the Project Manager.

11.4. Procedures for Reporting Adverse Events (AEs)

It is the responsibility of the Investigator or Sub-Investigator(s) to perform periodic assessments of all AEs as well as identifying SAEs. Safety surveillance and reporting starts as soon as the patient is enrolled in the clinical investigation. Safety surveillance and reporting will continue until the last follow-up visit has been performed, the subject is deceased, the subject concludes participation in the clinical investigation or the subject withdraws from the clinical investigation.

AEs, ADEs, SAEs and SADEs that occur during the study should be treated by established standards of care that will protect the life and safety of the subjects.

Any AEs/ADEs are to be reported as soon as possible after knowledge of the event. SAEs/SADEs must be reported to the Sponsor no later than 3 calendar days from the day the site personnel became aware of the event or as per the investigative site's local requirements, if the requirement is more stringent than

This confidential document is the property of Abbott and shall not be reproduced, distributed, disclosed or used without the express written consent of Abbott

Clinical Investigation Plan

3 calendar days. If an SAE/SADE is not reported within the required time, it will be considered a protocol deviation. The date the site staff became aware of an event meeting the criteria of an SAE must be recorded in the source documentation.

The Sponsor will ensure that all applicable events and device deficiencies are reported to the relevant authorities as per regulations. The sites should notify the Sponsor of reportable AEs by creating and saving the applicable CRF within the electronic data capture (EDC) system. The description of the AE, date of the AE, treatment and resolution of the AE will be reported, as applicable per regulations, to the relevant authorities. Additional information may be requested, when required, by the Sponsor in order to support the reporting or adjudication of AEs. The Investigator must notify the IRB, if appropriate, in accordance with national and local laws and regulations, of the AEs reported to the Sponsor. Additional information with regard to an adverse event should be updated within the appropriate CRF.

11.5. Criteria and Guidelines for Non-reportable Events

The following events are not reportable to the Sponsor:

- Symptoms of previously reported events and/or scheduled procedures, such as:
 - Cataract surgery
 - Colonoscopy
 - Flaring of gout (when gout is already reported/pre-existing condition)
 - Symptoms of HF (when primary HF is already reported)

11.6. Anticipated Adverse Events

11.6.1. Anticipated AEs

Events associated with the CardioMEMS™ PA Sensor or the implant procedure (in conjunction with RHC) or post-implantation complications are considered anticipated and include the following:

- Infection
 - Upper respiratory infection
 - Bronchitis
 - Pneumonia
 - Acute Bronchitis
 - Groin abscess
 - Methicillin-resistant staphylococcal aureus infection
 - Pulmonary Infiltration
 - Sepsis
- Arrhythmias
 - Ventricular tachycardia
 - Atrial fibrillation
 - Ventricular arrhythmia
 - Ventricular fibrillation
 - Atrial fibrillation with rapid ventricular response
 - Atrial flutter
 - Cardiac dysrhythmias
 - Tachycardia
 - Wide complex tachycardia
- Bleeding
 - Epistaxis

This confidential document is the property of Abbott and shall not be reproduced, distributed, disclosed or used without the express written consent of Abbott

Clinical Investigation Plan

- Hemoptysis
- GI bleed
- Bleeding
- Blood in stool
- Catheter site bleeding
- Catheter site ecchymosis
- Hematuria
- Nose bleeds
- Hematoma
 - Hematoma
 - Catheter site hematoma
 - Vessel puncture site hematoma
- Thrombus
 - Arterial thrombosis (limbs)
 - Blood clot
- Myocardial infarction
- Transient ischemic attack
- Stroke
- Death
- Sensor embolization
- Pulmonary artery perforation

11.6.2. Anticipated ADEs/SADEs

The following is a list of possible anticipated ADEs/SADEs:

- Hemoptysis
- Sensor not deploying
- Transient ischemic attack
- Atypical chest pain
- Sepsis leading to death
- Atrial arrhythmia leading to death
- Arterial embolism (upper extremity)
- PA (in-situ) thrombus
- Catheter site bleeding
- Catheter site ecchymosis
- Catheter site hematoma
- Vessel puncture site pain
- Cardiac monitoring abnormal
- Heart rate irregular
- Serum creatinine increased
- Dyspnea
- Congestive HF
- Ventricular tachycardia
- Dizziness
- Vessel perforation
- Sensor failure/malfunction
- Sensor migration

This confidential document is the property of Abbott and shall not be reproduced, distributed, disclosed or used without the express written consent of Abbott

Clinical Investigation Plan

- System not transmitting

Refer to the CardioMEMS™ PA Sensor and Delivery Catheter, Model CM2000 User Manual for more information. If it is not certain that an event meets the above definitions, contact the Project Manager.

For unexpected failure modes or unexpected adverse events, the site should follow their standard reporting practices for medical device reporting (MDR). As defined in 21 CFR 803, a MDR reportable event (or reportable event) means: An event that device user facilities become aware of that reasonably suggests that a device has or may have caused or contributed to a death or serious injury. A device user facility must report to sponsor and the FDA (no later than 10 days after awareness date) deaths and serious injuries that a device has or may have caused or contributed to, establish and maintain adverse event files, and submit summary annual reports to FDA.

STATISTICAL ANALYSIS

The data will be summarized using univariate statistics (e.g., N, mean, standard deviation, median, minimum and maximum) or frequency (e.g., N, %) as appropriate.

The primary time point for safety analyses is 24 months post enrollment. Enrollment is defined as having a successful Sensor implant. The primary time point for effectiveness analyses is 12 months post enrollment.

Unless otherwise specified, all statistical tests will be 2-sided with a significance level of 0.05.

12.1. Populations for Analysis

Safety Population: The Safety Population consists of all subjects who received a Sensor implant or underwent the implant procedure but were never implanted, regardless of study completion status. All safety analyses will be performed on the Safety population.

Subjects who are found not to have an appropriately sized pulmonary artery branch and did not receive the Sensor implant will be considered ineligible for the study. However, these subjects will be followed for 30 days for safety and all safety related data for these subjects will be provided.

Effectiveness Population: The effectiveness population consists of all subjects who received a Sensor implant regardless of study completion status. All effectiveness analyses will be performed on the effectiveness population.

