9.1.2. Sensor Failure Criteria

A Sensor failure occurs when no readings can be obtained from it after troubleshooting the system to rule out any problems with the external electronics.

EFFECTIVENESS ANALYSES

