12.6. Safety Analyses

The safety analyses will be performed using the Safety Population. The data will be summarized using univariate statistics (e.g., N, mean, standard deviation, median, minimum and maximum) or frequency (e.g., N, %) as appropriate.

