12.6.1. Primary Safety Endpoints

The primary safety analyses will be based on the following objective performance criteria: a) the lower limit of the two-sided 95% confidence interval on the freedom from device / system-related complication rate at 24 months is greater than 80% and b) the lower limit of the two-sided 95% confidence interval on the freedom from pressure sensor failure rate at 24 months is greater than 90%. These primary safety endpoints will be tested hierarchically in order to control for multiplicity. First, the freedom from device / system-related complication rate will be tested. If the result is statistically significant (i.e., $p < 0.050$), then the freedom from pressure sensor failure rate will also be tested for significance (i.e., $p < 0.050$). The study will be judged to have provided positive safety results if both tests of the primary safety analysis endpoints are statistically significant (i.e., $p < 0.050$).

Mathematically stated, the primary safety hypotheses are:

a) $H_0: P_{(\text{Freedom from device / system-related complications at 24 months})} \leq 80\%}$

$H_a: P_{(\text{Freedom from device / system-related complications at 24 months})} > 80\%$

b) $H_0: P_{(\text{Freedom from pressure sensor failure at 24 months})} \leq 90\%$

$H_a: P_{(\text{Freedom from pressure sensor failure at 24 months})} > 90\%$

Plotting and analysis of safety endpoints will also be displayed using Kaplan-Meier methods.

This confidential document is the property of Abbott and shall not be reproduced, distributed, disclosed or used without the express written consent of Abbott

Clinical Investigation Plan

Safety will also be assessed throughout the study by the frequency of Adverse Events (AEs), Adverse Device Effects (ADEs), Serious AEs (SAEs), and Serious Adverse Device Effects (SADEs), and device / system-related complications by relationship to the device via Medical Dictionary for Regulatory Activities (MedDRA) system organ classification. Physical examination, and subject survival data through 24 months will be tabulated across study period assessments.

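### The primary sensor-failure test is assigned to a population that includes subjects with no sensor; it should be analysed in implanted subjects only

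*Combined protocol and SAP*

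**What the plan says.** Section 12.1 defines the population: "The Safety Population consists of all subjects who received a Sensor implant or underwent the implant procedure but were never implanted". It adds, without exception, "All safety analyses will be performed on the Safety population". Section 12.6, which heads the primary safety tests, repeats the assignment: "The safety analyses will be performed using the Safety Population". Both synopses (main study and sub-study) say the same.

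Section 12.6.1 sets the second primary safety criterion: "the lower limit of the two-sided 95% confidence interval on the freedom from pressure sensor failure rate at 24 months is greater than 90" percent. It names no other denominator. Section 9.1.2 defines the event: "A Sensor failure occurs when no readings can be obtained from it after troubleshooting the system".

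The next paragraph of 12.1 deals with small arteries: "Subjects who are found not to have an appropriately sized pulmonary artery branch and did not receive the Sensor implant will be considered ineligible". It then says that "these subjects will be followed for 30 days for safety and all safety related data for these subjects will be provided". It does not say whether they are inside the Safety Population or reported alongside it.

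The introduction to section 12 and Appendix J define enrollment as a successful implant, and section 12 times the primary safety analyses at 24 months from enrollment.

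**The concern.** The event in 9.1.2 needs an implanted sensor. A subject who had the procedure but left without a sensor was never at risk of it, yet the stated analysis population contains that subject. Nor does such a subject have a time zero from which 24 months could be counted.

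The protocol expects such subjects. The 7 mm branch criterion (inclusion criterion 7) can be assessed only during the right heart catheterization, sections 6 and 8.2 provide a category for subjects who consented but were not implanted, and 11.6.2 lists non-deployment of the sensor as an anticipated event. Because the 1200 enrolled are all implanted by definition, never-implanted subjects come on top of them.

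The Safety Population suits the complication endpoint, where harm from an unsuccessful procedure should count. For sensor reliability it is the wrong denominator. At stake are the error rate of a confirmatory safety claim and the reliability figure that goes into the device labeling.

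**Working it through.** **Inputs from the documents.** Null proportion 0.90; exact two-sided one-sample binomial test at 0.05, so 0.025 in the direction of success; 663 subjects for more than 90% power at 0.90 + 0.035 = 0.935 (section 12.2); 1200 enrolled, all implanted.

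**Input assumed.** The share *f* of the analysed set that had the procedure but no implant. The documents give no figure, so a range is shown.

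**Step 1: the plan's own figure.** With n = 663, the smallest success count whose upper-tail probability under Bin(663, 0.90) is at most 0.025 is 612, so at most 51 failures. The error rate is 0.0245 and power at 0.935 is 0.905. The smallest n that reaches 90% power is 663, so the plan's number reproduces exactly.

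**Step 2: direction.** If never-implanted subjects count as failure-free, a true proportion *p* among implanted subjects appears as *p* + *f*(1 − *p*). At *p* = 0.90 and *f* = 0.05 this is 0.90 + 0.05 × 0.10 = 0.905. The shift is upward for every *f* > 0, by 0.1 percentage point per 1% never implanted.

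**Step 3: size under that rule.** Take *n* implanted subjects, all observed to 24 months, and add *m* = *n f*/(1 − *f*) never-implanted subjects. Apply the same exact rule to *N* = *n* + *m* to find the largest allowed number of failures *c*. The false-pass probability is P(Bin(*n*, 0.10) ≤ *c*).

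| *f* | 1200 implanted: *m* added | *c* | False pass | 663 implanted: *m* added | *c* | False pass |
|---|---|---|---|---|---|---|
| 0% | 0 | 99 | 2.2% | 0 | 51 | 2.5% |
| 1% | 12 | 100 | 2.8% | 7 | 51 | 2.5% |
| 2% | 24 | 101 | 3.5% | 14 | 52 | 3.4% |
| 3% | 37 | 102 | 4.4% | 21 | 52 | 3.4% |
| 5% | 63 | 105 | 8.0% | 35 | 54 | 6.0% |
| 8% | 104 | 109 | 15.6% | 58 | 56 | 10.0% |

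These figures are for the sensor-failure test taken alone. Under the hierarchy in 12.6.1 it is reached only after the complication test succeeds.

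**Step 4: size under other follow-up rules.**
- Proportion among subjects with 24-month status: never-implanted subjects drop out and the effect is zero.
- Kaplan-Meier, with never-implanted subjects censored at 30 days: for *f* = 5% and 10% failures spread evenly over 24 months, only the first month's failures (0.10/24) are diluted. The estimate rises by about 0.05 × 0.10/24 = 0.0002, or 0.02 percentage point.

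**The case against.** The strongest reply is that nothing in the plan says a never-implanted subject counts as failure-free. The endpoint is a 24-month status and these subjects can have none. Section 12.3 bars imputation unless specified. Section 12.2 allows for attrition around the 663, which suggests a denominator of subjects with 24-month data, and on that basis the effect disappears. This stands, and it makes the inflation conditional. It does not remove the defect, because the plan commits to no such rule: the sizing test is a simple binomial, Kaplan-Meier is described only as an additional display, Appendix L reports sensor failures as a count and percentage, and the Safety Population applies whether or not a subject completed the study.

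It also stands that the illustration in step 3 is stylised. It treats all 1200 (or 663) sensors as fully observed. If subjects with short follow-up really were counted as successes, early leavers among the implanted would matter far more. With the stated 49.1% attrition, evenly spread or at constant hazard, and a constant failure hazard giving 10% at 24 months, observed failures are only about 7.3-7.6%. The false-pass probability is then 82-90% before any never-implanted subject is added, and 87-93% with 2% added. The denominator question is therefore tied to the handling of incomplete follow-up.

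A reader might infer that subjects ruled out on the angiogram are definitely in the denominator. The text does not settle that. Section 12.1 gives them a separate paragraph, and section 8.2 has only patients with a suitable branch going on to sensor implant. Section 6, however, describes the implant procedure as done together with the catheterization, so they could be said to have undergone it. If they are excluded, failed attempts in suitable arteries remain expressly included, as a smaller group of unknown size.

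**Conclusion.** The point holds as a wrong denominator in the stated rule. Read literally, 12.1 and 12.6 put never-implanted subjects into a primary endpoint that they cannot experience and for which they have no time point. The status of angiogram-ineligible subjects is ambiguous.

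A reader might go further and conclude that the 90% criterion is certainly easier to pass than stated. The documents do not support that. It follows only if never-implanted subjects count as failure-free in a simple proportion, which the plan neither says nor rules out. Under that reading, and with full 24-month observation of implanted sensors, the inflation is small for 1-3% never implanted and material at 5% or more. The 5% and 8% rows are illustrations, since no implant-failure share is given. With evaluable-only or Kaplan-Meier handling the effect is about zero.

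The change is still worth making: the test is confirmatory, the right analysis set already exists, and naming it removes this question under every follow-up rule.

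**What to change.** In 12.1, 12.6/12.6.1 and the synopsis, state that freedom from pressure sensor failure is analysed in subjects who received a Sensor implant, which is the set already defined as the Effectiveness Population. Keep the Safety Population, with attempted but unsuccessful implants, for device/system-related complications. Qualify the sentence that sends all safety analyses to the Safety Population, including its repeat in the sub-study synopsis. State in 12.1 whether angiogram-ineligible subjects belong to the Safety Population or are reported separately.

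This does not by itself settle how implanted subjects with incomplete follow-up enter the 24-month proportion; that rule needs its own statement.

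The cost is a few sentences, with no new data or patients. The downside is that the sensor-failure result may become slightly less favourable.

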12.2. Sample Size Considerations

Effectiveness Sample Size Determination

For the primary effectiveness endpoint of HF hospitalization rate during 1 year, 300 patients will provide greater than 90% power to meet the efficacy goal (upper confidence limit less than the HF hospitalization rate in the year prior to enrollment), using a one-sample, two-sided Poisson confidence interval with alpha of 0.05.

Safety Sample Size Determinations

For the two-year primary safety endpoint of freedom from device-related complications, using an exact two-sided test for one-sample binomial proportions with alpha of 0.05, a sample size of 619 subjects will provide greater than 90% power to detect a difference as small as 5% from the null proportion rate of 0.80 (i.e., objective performance criterion of 80%). For sensor failures at 2 years, a sample size of 663 subjects provides greater than 90% power to detect a difference as small as 3.5% from the null proportion rate of 0.90 (i.e., objective performance criterion of 90%).

This confidential document is the property of Abbott and shall not be reproduced, distributed, disclosed or used without the express written consent of Abbott

Clinical Investigation Plan

Thus, the sample size for this study is driven by the safety endpoints. The 2 year attrition rate in CHAMPION was 49.1% (228/550). To ensure sufficient patients are enrolled to adequately evaluate safety and efficacy, 1200 subjects will be enrolled.

Note that at least 35% of the 1200 enrolled patients (420) must be women resulting in approximately 206 women completing the trial (assuming a 49% attrition rate). This sample size will provide greater than 90% power to meet the goal for effectiveness. Regarding freedom from device-related complications and freedom from sensor failures, 206 women will provide greater than 90% power to detect a difference as small as 0.06 from the null proportion rate of 0.90.

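### Section 12.2 gives power for each safety endpoint alone; under the gated both-must-pass rule in 12.6.1, power with 663 evaluable subjects is about 83% at the smallest stated differences

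*Combined protocol and SAP*

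**What the plan says.** Section 12.2 treats the two primary safety endpoints separately, "using an exact two-sided test for one-sample binomial proportions with alpha of 0.05".

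- **Complications:** "a sample size of 619 subjects will provide greater than 90% power to detect a difference as small as 5" percentage points from the "null proportion rate of 0.80 (i.e., objective performance criterion of 80"%).
- **Sensor failure:** "a sample size of 663 subjects provides greater than 90% power to detect a difference as small as 3.5" percentage points from the "null proportion rate of 0.90 (i.e., objective performance criterion of 90"%).

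The section then says that the safety endpoints drive the study size. It allows for attrition and sets enrolment at 1200. It gives no power for the two endpoints together.

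Section 12.6.1 fixes the direction of each test through the lower confidence limit; for sensor failure the requirement is that "the lower limit of the two-sided 95% confidence interval on the freedom from pressure sensor failure rate at 24 months is greater than 90"%. It orders the tests: complications come first, and only if that result is significant, "then the freedom from pressure sensor failure rate will also be tested for significance". It then defines success: "The study will be judged to have provided positive safety results if both tests of the primary safety analysis endpoints are statistically significant".

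Section 12.1 runs all safety analyses on the Safety Population, which keeps subjects whether or not they complete the study.

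**The concern.** The power in 12.2 belongs to two free-standing tests. The design in 12.6.1 is a gated sequence with a both-must-pass criterion. Under that rule a sensor-failure claim requires the complication test to succeed as well, so claiming sensor failure and declaring safety positive are the same event. Its probability cannot exceed the smaller of the two stand-alone powers, and in general it is lower than both.

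At stake is what a reader of 12.2 takes the study's chance of a positive safety conclusion to be. The section presents the safety endpoints as the basis of the sample size, and the figures it gives for them are two powers above 90%. It is natural to conclude that, at those differences, the safety conclusion would be missed less than one time in ten. With 663 evaluable subjects it would be missed about one time in six.

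**Working it through.** **Inputs.** From 12.2: exact one-sample binomial tests, two-sided alpha 0.05, so at most 0.025 in the upper tail; nulls 0.80 and 0.90; differences of 5 and 3.5 points, giving true rates of 0.85 and 0.935; sample sizes 619 and 663; enrolment 1200; attrition printed as 49.1% (228/550). From 12.6.1: the order of testing and the requirement that both pass.

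**Formula.** For each endpoint, find the smallest count r with P(X ≥ r | n, null) ≤ 0.025. Power is P(X ≥ r | n, true rate).

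**Step 1: the plan's own figures.**
- Complications, n = 619: r = 515, tail 0.0244, power 90.4%.
- Sensor failure, n = 663: r = 612, tail 0.0245, power 90.5%.

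Both reproduce, and 619 and 663 are the first sample sizes at which exact power reaches 90%. The method therefore matches the sponsor's.

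**Step 2: both tests on 663 subjects.**
- Complications: r = 551, tail 0.0238, power 0.9204.
- Sensor failure: r = 612, power 0.9048.
- Joint, if independent: 0.9204 × 0.9048 = 0.833.

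**Step 3: dependence.** The documents give no correlation between the two events. Fixing the failure probabilities at 0.15 and 0.065 and varying their overlap from none to complete (every sensor failure is also a complication), a multinomial simulation with 2,000,000 runs per setting gives joint power from 83.0% to 86.0%. No feasible overlap brings it to 90% at n = 663.

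**Step 4: a better complication-free rate.** At n = 663, sensor rate 0.935, independence:

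| True complication-free rate | Complication power | Joint power |
|---|---|---|
| 0.85 | 92.0% | 83.3% |
| 0.86 | 98.4% | 89.1% |
| 0.87 | 99.8% | 90.3% |

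**Step 5: the number analysed.** True rates 0.85 and 0.935, independence:

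| Evaluable subjects | Source | Complications | Sensor failure | Joint |
|---|---|---|---|---|
| 611 | 1200 × (1 − 0.491) | 88.9% | 86.6% | 77.0% |
| 663 | 12.2 | 92.0% | 90.5% | 83.3% |
| 702 | 1200 × (1 − 228/550) | 93.1% | 91.0% | 84.8% |
| 776 | first n with joint power of 90% | 95.5% | 94.3% | 90.1% |
| 1200 | all enrolled count | 99.5% | 99.3% | 98.8% |

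The rows for 611 and 702 differ because the printed percentage and the printed fraction disagree (228/550 is 41.5%, not 49.1%). That is a separate matter. The drop to 77.0% at 611 is partly a smaller sample and not the effect of gating alone: the stand-alone powers there are already below 90%.

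**The case against.** The strongest reply is that nothing printed in 12.2 about these two powers is wrong. It gives power endpoint by endpoint, both figures reproduce, and it never claims 90% for the two together. That stands: the point concerns a quantity left out, and 619 and 663 need a label, not a correction.

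Second, the differences in 12.2 are the smallest to be detected, not the performance expected. The documents state no expected complication-free or failure-free rate. That also stands. The 83% applies when both rates sit at those minimum differences together, and Step 4 shows how quickly it improves.

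Third, enrolment is 1200 and the Safety Population keeps non-completers. Taken at face value, that gives 98.8%. A reader might infer from the 83% that the trial is underpowered for safety; the documents do not support that, because they do not fix how many subjects count at 24 months. Nor do they support the opposite inference that the issue disappears. Section 12.2 itself discounts 1200 for attrition, and it counts women by those completing (about 206 of 420). On that basis joint power is 77.0% or 84.8%, depending on which attrition figure is meant.

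Fourth, hierarchical testing needs no alpha adjustment. True, but the ordering protects type I error and does nothing for power.

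Finally, Appendix A anticipated complete enrolment by December 2017 and this version is dated 19 February 2018, so a restated power would not alter recruitment if that timeline held. That limits the consequence. It does not remove the value of describing correctly the figure on which the study size rests.

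**Conclusion.** The point holds in a conditional form. With 663 evaluable subjects and true rates of 0.85 and 0.935, the rule in 12.6.1 gives about an 83% chance of a sensor-failure claim, and hence of overall safety success (83% to 86% across feasible overlap), where 12.2 shows only a stand-alone figure above 90%. The result rests on exact tests with at most 0.025 in the upper tail, both endpoints analysed on the same 663 subjects, and independence for the 83.3% itself; the shortfall from 90% does not depend on independence.

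It is not a forecast for the trial. Over the evaluable numbers the documents allow, joint power at the same rates runs from 77.0% to 98.8%, and 12.2 does not let a reader tell which applies. Type I error, the tests and the success rule are unaffected.

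**What to change.** In section 12.2:

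1. Label 619 and 663 as stand-alone power for each endpoint.
2. State the joint power under the 12.6.1 rule: with 663 evaluable subjects and true rates of 0.85 and 0.935, about 83% assuming independence, and 83% to 86% over feasible overlap.
3. State the evaluable number that the 24-month safety analysis will use, and give the joint power for it. This requires reconciling the attrition allowance in 12.2 with the Safety Population in 12.1.

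The change is a few sentences. It adds no enrolment and leaves endpoints, tests, alpha and success criterion as they are. The only downside is a less favourable stated power.

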13.4. Sub-study Sample Size

The Control group HF hospitalization rate for Part 1 of the CHAMPION study at 1 year was 0.75.

Using an exact one-sample, 2-sided Poisson 95% confidence interval with alpha of 0.05, 114 patients will provide 85% power to show a difference between the estimated Treatment rate of 0.52 and the Control rate of 0.75. Likewise, 130 patients are required to achieve 90% power to show a difference between the estimated Treatment rate of 0.52 and the Control rate of 0.75.

The 2 year attrition rate in CHAMPION was 49.1%, therefore 256 patients $(130/(100\%-49.1\%)) = 256$ is the minimum sample size for this analysis. However, the Independent Committee will identify all patients that are optimally managed and are clinically similar to the Control group in CHAMPION. Therefore, the eligible patients for this sub-cohort and the resultant sample size may be greater.

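### Section 12.2 gives CHAMPION attrition as 49.1% beside 228/550, which is 41.5%; whether 1200 enrolled delivers 619 and 663 depends on which figure is right

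*Combined protocol and SAP*

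**What the plan says.** Section 12.2 sizes the two 24-month safety endpoints with an exact two-sided one-sample binomial test at alpha 0.05.

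- Complications, null 0.80: "a sample size of 619 subjects will provide greater than 90% power to detect a difference as small as 5" percentage points.
- Sensor failure, null 0.90: "a sample size of 663 subjects provides greater than 90% power to detect a difference as small as 3.5" percentage points.

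It says that safety drives the sample size, and continues: "The 2 year attrition rate in CHAMPION was 49.1% (228/550"). The next sentence is "To ensure sufficient patients are enrolled to adequately evaluate safety and efficacy, 1200 subjects will be enrolled". No calculation joins the attrition rate to 1200.

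The percentage is then reused. For the 420 women, Section 12.2 gives a figure "resulting in approximately 206 women completing the trial (assuming a 49% attrition rate"). Section 13.4 says "The 2 year attrition rate in CHAMPION was 49.1%, therefore 256 patients", obtained by dividing 130 by one minus that rate. The fraction 228/550 appears once and feeds no other figure.

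**The concern.** The percentage and the fraction cannot both be right as printed. Section 4.2 also gives 550 as the number enrolled in CHAMPION, so the denominator agrees with the rest of the document.

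The mismatch falls at the step that turns the required numbers into enrolment. If the two rates led to the same conclusion, this would be a typing error and no more. They do not: the attrition levels at which 1200 stops delivering 619 and 663 both lie between 41.5% and 49.1%. A reader therefore cannot tell from the plan whether the stated power is supported. Section 12.6.1 requires both safety tests to succeed, so the weaker endpoint matters.

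**Working it through.** **Inputs.** From 12.2: 228/550, 49.1%, 1200 enrolled, 619 (0.80 against 0.85), 663 (0.90 against 0.935), 420 women, 49%. From 13.4: 130 and 256. Power is exact binomial with an upper-tail level of 0.025, which is the direction that counts for these hypotheses.

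**1. The plan's targets reproduce.**
- n = 619: reject at 515 or more event-free subjects; power 90.4%.
- n = 663: reject at 612 or more; power 90.5%.

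Each is the first n at which exact power reaches 90%. The targets are sound, and the problem is confined to attrition.

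**2. The attrition rate does not reproduce.**
- 228/550 = 0.4145. The complement is 322/550 = 0.5855.
- 0.491 × 550 = 270.05, and 270/550 = 0.4909.

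**3. Completers and enrolment under each rate.**

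| | Attrition 49.1% | Attrition 228/550 = 41.5% |
|---|---|---|
| Completers from 1200 | 1200 × 0.509 = 611 | 1200 × 322/550 = 702 |
| Enrolment for 619 completers | 619/0.509 → 1217 | 619/0.5855 → 1058 |
| Enrolment for 663 completers | 663/0.509 → 1303 | 663/0.5855 → 1133 |
| Completer-only power, complications | 88.9% | 93.1% |
| Completer-only power, sensor failure | 86.6% | 91.0% |

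Neither rate turns 663 into 1200.

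**4. Break-even attrition for 1200 enrolled.**
- To keep 619: 1 − 619/1200 = 48.4%.
- To keep 663: 1 − 663/1200 = 44.75%.

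**5. Sensitivity to the discreteness of the exact test.** Over n = 608 to 614, power runs from 88.3% to 90.0% for complications and from 85.9% to 87.3% for sensor failure. The first is marginal; the second stays below 90% throughout.

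**6. Upper bound.** If all 1200 contributed to the 24-month proportions, power would be 99.5% and 99.3%.

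**7. Women.** 420 × 0.49 = 205.8, so the stated 206 is the number lost. Completers are 420 × 0.51 = 214, or 420 × 322/550 = 246 at 41.5%. Power for 0.90 against 0.96 is 92.8% at 206, 91.0% at 214 and 96.0% at 246.

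**8. Sub-study.** 130/0.509 = 255.4, so 256 is correct at 49.1%. At 41.5% the same formula gives 130/0.5855 = 222.05, rounded up to 223.

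**The case against.** The strongest reply is that the shortfall is doubly conditional: 49.1% must be the right rate, and early leavers must drop out of the analysis. Section 12.2 calls 619 and 663 subjects, not completers, and never says that 1200 is the target divided by the retained fraction. Section 12.1 defines the Safety Population as everyone who received a sensor or "underwent the implant procedure but were never implanted, regardless of study completion status". Section 12.6.1 adds: "Plotting and analysis of safety endpoints will also be displayed using Kaplan-Meier methods". True power could therefore lie anywhere between the 611 case and the 1200 case.

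This stands as a limit on size: 611 is a lower bound, not a forecast. It does not remove the point. The plan reasons in completers for the women in 12.2 and inflates for attrition in 13.4, and it does not say how early leavers enter the 24-month proportion.

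Four smaller objections are fair:

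- The complications result is within the saw-tooth of the exact test; n = 623, above the plan's own 619, gives 89.1%.
- Sensor-failure power at n = 611 passes 90% again if the true rate is 93.7% rather than 93.5%.
- The slip in the women's count changes no decision.
- 49.1% would also fit 228 over about 464 (228/0.491 = 464.4). Nothing in the documents supports that denominator, but the check should cover it as well as the numerator.

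**Conclusion.** The concern holds. The printed rate and the printed fraction contradict each other, and the documents do not settle which is wrong. Repeated use of 49% and 49.1% shows which figure was carried forward, not which is correct.

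On the plan's own completer reasoning, 1200 misses both targets at 49.1% (by 8 and by 52 subjects) and exceeds both at 41.5%. The loss of power is clear for sensor failure, about 3 to 4 points below the stated 90%, and marginal for complications. These figures assume completers only, the stated alternatives of 0.85 and 0.935, and CHAMPION attrition carrying over to this study.

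The count of 206 women completing is also wrong, without consequence for the power claim. The matter should be corrected, but it does not put the design in doubt.

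**What to change.** Check the CHAMPION two-year disposition (numerator and denominator), then make percentage and fraction agree in 12.2 and 13.4 and show how 1200 was reached.

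- **If 49.1% of 550 is confirmed:** print 270/550; state 611 completers, power of about 89% for complications and 87% for sensor failure, and 214 women completing. The 256 in 13.4 stands.
- **If 228/550 is confirmed:** print 41.5%; state 702 completers, power of about 93% and 91%, and 246 women completing. Revise the derivation in 13.4, where the formula would give 223; the existing minimum of 256 would remain sufficient.

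In either case, label the power as completer-only, because the Safety Population includes subjects regardless of completion.

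The cost is one look-up and wording in two sections. Enrolment, endpoints and visits do not change. If 49.1% is confirmed, the stated completer-only power becomes slightly less favourable.
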